## **Revision Control**

Protocol version	Updated SAP version number	Section number changed	Description of change	Date changed
V3.1	V1.0			

## **Abbreviations and Definitions**

TIPS	Transjugular intrahepatic portosystemic		
	shunt		
GO	Glue Obliteration		
GOV	gastro-esophageal varices		
MELD	Model of End stage Liver Disease		
GV	Gastric Varices		
eCRF	electronic Case Report Form		

# Section 2: Introduction

## **Background and Rationale**

TIPS could have a place to prevent rebleeding after gastric variceal bleeding. It effectively prevents a rebleeding related to portal hypertension as well as numerous complications of cirrhosis. In the single randomized trial comparing glue obliteration to TIPS, TIPS better prevented rebleeding but was associated with a high risk of hepatic encephalopathy and showed no benefit in survival (50). However, survival and post TIPS encephalopathy improved in recent studies using early PFTE-covered TIPS placement. We therefore

assume that early TIPS is the strategy of choice in the management of gastric variceal bleeding. The objective of this study will be to compare demonstrate the superiority of TIPS placement within 72 hours to versus iterative glue obliteration in preventing rebleeding or death after a non-type 1 gastroesophageal gastric variceal bleeding in cirrhotic patients initially treated by glue obliteration.

Our study will be the first large randomized multicenter study to evaluate the 12-month benefit of early TIPS (survival free of rebleeding) in cirrhotics with GV bleeding. In the study by Lo et al., conducted between 1999 and 2004, the TIPS procedure was different from that currently recommended (notably uncovered TIPS) and patients were randomized 3 days after bleeding

control. Thus, rate of early death or rebleeding could not be evaluated and rebleeding within 12 months in the TIPS group was high compared with recent publications. Moreover, in recent studies with early covered TIPS placement, the occurrence of encephalopathy was not different between TIPS group and control group (31, 32, 49). By analogy with early TIPS for the management of esophageal varices, we hypothesize that patients with GV bleeding will benefit from early TIPS. Our trial will evaluate the rate of 12-month survival free of rebleeding and should permit to define the best strategy for the management of GV bleeding.

## **Objectives**

#### **Primary objective:**

To demonstrate the efficacy of an "early tips" strategy over glue obliteration (standard treatment) in preventing bleeding recurrence or death at one year after a non type 1 gastroesophageal gastric variceal bleeding in cirrhotic patients initially treated by glue obliteration.

#### **Secondary objectives:**

Demonstrate the efficacy of an "early-TIPS" strategy to reduce:

- 1/ All-cause mortality rate at Days 42 and 365.
- 2/ Liver related mortality rate at Days 42, 90, 180 and 365.
- 3/ Rebleeding rate at Days 42, 90, 180 and 365.
- 4/ Cumulative incidence of complications of cirrhosis at Day 365.
- 5/ Transfusion requirements at Days 42 and 365.

#### Describe:

- 6/ TIPS and glue obliteration complications.
- 7/ Compliance in each group.
- 8/ The evolution of liver function at 6 months in each group.
- 9/ The need for hospitalization in each group during follow-up.
- 10/ Describe the number of infections and their localizations.

## **Section 3: Study Methods**

## 3.1 Trial Design

This is an open label, multicenter, randomized, 2-arm parallel-group in a 1:1 ratio, trial to investigate the superiority of an "early tips" over glue obliteration in cirrhotic patients bleeding from gastric varices (non GOV1). The main end-point is death or clinically significant rebleeding during the 12-month follow-up, and randomized patients are followed until the end of the 12-month study period.

#### Early TIPS procedure in experimental arm (Group A):

- TIPS using covered stent will be placed under general anesthesia and with radioscopic guidance by experts.
- The procedure should be performed as soon as possible after randomization and before Day 4.
- Portal pressure should be taken at the time of TIPS insertion, with a goal of hepatic venous pressure gradient of less than 12 mmHg at the end of the procedure.
- Embolization of collaterals will not be authorized in the present study.

## Glue obliteration procedure in control arm (Group B):

- Filling of varice(s) with tissue adhesive under endoscopic guidance will be initially performed in all patients under general anesthesia. The use of a Doppler EUS will be at the discretion of the practitioner.
- Endoscopic control (and further glue obliteration session if necessary) will be performed in the group B between day-5 and day-8 after the initial bleeding. A new session will then be proposed at days 42+/-7, 90+/-14, 180+/-14 and 365+/-14.
- Endoscopic reports will be systematically collected. The report should specify the topography and size of varices (if possible, a picture will be collected), the type of glue, the volume injected as well as the proportion of Lipiodol.
- In the case of coexistence of esophageal varices, the latter will be systematically treated during the same endoscopic session by band ligation.
- In patients randomized to group B the decision of "salvage TIPS" will be left to the discretion of the investigator and will be then considered as a failure of the endoscopic procedure.
- When placing TIPS for another indication during follow-up in the group B, the patient will be censured at the date of installation of the device.
- In the absence of contraindication, a non-selective beta-blocker treatment will be proposed in the group B according to the recommendations of the Baveno VI Consensus Workshop 2015 (14).

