## 3.3 Sample size

The sample size is calculated with a projected rate of composite event of failure at 12 months of 15% in the group "TIPS" [estimated from Garcia Pagan, New Engl J Med 2010] versus 40% in the group « glue» [estimated from Hou, Gastrointest Endosc 2009].

A number of 52 patients in each group will achieve 80% power to detect TIPS superiority using a one-sided logrank test at a 0,050 significance level, with a proportion dropping out of both groups of 10%.

Total number of scheduled patients recruited or observations collected: 104.

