## **Section 6: Analysis**

#### 6.1 Outcome Definition

## Primary endpoint

Death (all cause) or clinically significant rebleeding (upper gastrointestinal bleeding whatever its origin, with event date) during the one-year follow-up.

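### The SAP does not say whether a discretionary salvage TIPS in the glue arm is a primary endpoint event, and its wording lets one be coded as a control-only failure

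*SAP*

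**What the plan says.** Section 3.1 describes the design: "This is an open label, multicenter, randomized, 2-arm parallel-group in a 1:1 ratio". Its list of control-arm procedures has two rules for a TIPS placed in group B.

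- The decision to place a salvage TIPS "will be left to the discretion of the investigator and will be then considered as a failure of the endoscopic procedure".
- A group B patient who receives a TIPS for a different reason is censored on the day it is placed.

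The early-TIPS procedure list for group A has no counterpart to either rule. The SAP does not define salvage and does not require a qualifying rebleed before it.

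The primary endpoint in section 6.1 is "Death (all cause) or clinically significant rebleeding (upper gastrointestinal bleeding whatever its origin, with event date) during the one-year follow-up". Section 3.1 agrees: "The main end-point is death or clinically significant rebleeding during the 12-month follow-up". So does the primary objective in section 2. Section 3.3 uses a different label for the same outcome. It plans on a "projected rate of composite event of failure at 12 months of 15% in the group" allocated to TIPS, "versus 40% in the group" allocated to glue.

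Section 6.2 (primary composite endpoint) does not mention salvage TIPS. Nor does section 6.3 (survival analysis), which censors only at end of follow-up, loss to follow-up and liver transplantation. Section 4.3 keeps crossovers in their randomized arm.

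**The concern.** The two group B rules stand side by side. The second is plainly a time-to-event rule, because it names censoring and a date. The first can easily be read as its partner: one kind of TIPS censors the patient, the other fails the patient. Section 3.3 supports that reading by using the word failure for the primary composite.

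Two programmers could therefore code the same control patient differently. One who follows section 3.1 records an event at the salvage TIPS. One who follows section 6.1 records nothing and continues follow-up.

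On the first coding, an unblinded, discretionary decision becomes a primary event in one arm only. That pushes the comparison towards TIPS, and the result no longer answers the stated objective of preventing rebleeding or death. If the choice is left until after database lock, it can also be made with the data in view.

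**Working it through.** **The plan's own figure.** Inputs from section 3.3: 40% against 15% at 12 months, 80% power, one-sided 0.05, 10% dropout, 52 per arm. A one-sided two-proportion formula gives (1.645·√(2·0.275·0.725) + 0.842·√(0.40·0.60 + 0.15·0.85))² / 0.25² = 38.4. With continuity correction this is 38.4/4 · (1 + √(1 + 4/(38.4·0.25)))² = 46.1, so 47 per arm. Then 47·1.1 = 51.7, or 52; 47/0.9 = 52.2, or 53. So 52 is reproduced to within one patient, though by a two-proportion formula and not by a log-rank formula. Nothing in it depends on salvage TIPS.

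**Which patients are affected.**

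| Group B patient | Section 6.1 | Section 3.1 read as an event rule |
|---|---|---|
| Qualifying rebleed, then salvage TIPS | event at the bleed | event at the bleed |
| Salvage TIPS, no qualifying bleed or death by Day 365 | no event | event at TIPS |
| Salvage TIPS, qualifying bleed or death later | event at the later date | event at TIPS, earlier |
| TIPS for another indication | follow-up continues | censored (adjacent bullet) |

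Only the second and third rows matter for salvage TIPS. The fourth row shows that an unblinded label, salvage or other indication, decides between failure and censoring.

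**Size if salvage TIPS is counted.** Let p be the true 12-month risk of death or rebleeding, equal in both arms, and s the risk of a salvage TIPS without a prior qualifying bleed, in controls only. Assuming independent exponential times:

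- apparent control risk = 1 − (1 − p)(1 − s)
- apparent hazard ratio = ln(1 − p) / ln[(1 − p)(1 − s)], although the true value is 1

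Example with p = 0.40 and s = 0.10: control risk = 1 − 0.60·0.90 = 46%; hazard ratio = ln 0.60 / ln 0.54 = 0.83.

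The false-win column is simulated: log-rank test, 52 per arm, 10% dropout, proportion with z < −1.96 in favour of TIPS. This is the TIPS side of the two-sided 0.05 test in section 4.1. With s = 0 it is about 2.5%.

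| p | s | Apparent control risk | Apparent HR | False TIPS win |
|---|---|---|---|---|
| 40% | 5% | 43% | 0.91 | about 5% |
| 40% | 10% | 46% | 0.83 | about 9% |
| 40% | 15% | 49% | 0.76 | about 15% |
| 25% | 5% | 28.75% | 0.85 | about 6% |
| 25% | 10% | 32.5% | 0.73 | about 13% |
| 25% | 15% | 36.25% | 0.64 | about 23% |
| 15% | 5% | 19.25% | 0.76 | about 8% |
| 15% | 10% | 23.5% | 0.61 | about 19% |
| 15% | 15% | 27.75% | 0.50 | about 35% |

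Dropping the dropout assumption moves these by at most about two points. The values 40% and 15% for p are the two planning rates in section 3.3; 25% is an intermediate assumption. All values of s are assumptions.

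Few patients are needed. Three extra control events are 3/52 = 5.8 percentage points, against a planned difference of 40 − 15 = 25 points.

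**The case against.** The strongest reply is that no sentence in the SAP makes salvage TIPS a primary event. Section 3.1 says failure of the endoscopic procedure, not failure on the primary endpoint. Elsewhere the SAP uses failure for procedures: secondary endpoint 6 lists technical failure in both arms, and the per-protocol definition refers to TIPS failure. Where section 3.1 intends a time-to-event consequence it says so and gives a date; the salvage bullet does neither. The definition in section 6.1 is the operative one, and sections 2 and 3.1 agree with it. The bar for a qualifying rebleed is also low, since recurrent melena or hematemesis with hospital admission is enough. Many salvage TIPS may therefore follow an event already counted.

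Most of this stands. A reader might infer that the control arm will collect primary failures that the TIPS arm cannot have. The document does not support that: it is one possible reading, and under section 6.1 the effect is zero. How often salvage TIPS would occur without a qualifying bleed is unknown, and the protocol may define the term.

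The reply does not remove the ambiguity. Technical failure of glue obliteration is undefined and listed with procedural complications, so a later discretionary TIPS does not clearly belong there. Section 3.3 still uses the same word for the primary composite, and neither 6.2 nor 6.3 settles the coding.

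**Conclusion.** The concern holds as an unresolved coding rule for the primary endpoint, not as a demonstrated bias. Section 3.1 can be read as making a salvage TIPS without a qualifying bleed a control-only primary event; section 6.1 does not allow that; the analysis sections are silent.

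If section 6.1 is followed, or a qualifying bleed always comes first, there is no inflation. If salvage TIPS is counted, the chance of a false TIPS win rises from 2.5% to between about 5% and 35% over the ranges shown. It is higher when the true event risk is lower. These figures rest on assumed salvage risks, independent exponential times, 52 per arm and no true treatment difference. They show what is at stake and do not forecast the result. The matter should be settled before analysis because it concerns the primary comparison and costs little to close.

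**What to change.** Add one statement to section 3.1 and repeat it in sections 6.2 and 6.3. It should say that a salvage TIPS in group B is neither a primary endpoint event nor a censoring point. Only deaths and rebleeds meeting the section 6.1 definitions count, each dated at its occurrence. The patient stays in group B and is followed to Day 365.

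Keep failure of the endoscopic procedure as a descriptive outcome for group B, reporting the number of salvage TIPS, their timing and the reasons. In section 3.3, name the primary outcome as section 6.1 does.

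In the same edit, reconcile the group-B-only censoring at TIPS for another indication with the as-randomized rule in section 4.3 and the censoring list in section 6.3. At present the censoring applies to one arm, depends on an unblinded label, and is missing from section 6.3.

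The cost is SAP wording only. The sample size is unaffected and no change to the indication for salvage TIPS is implied. The one small downside is that the observed control event rate may be slightly lower than if salvage TIPS were counted.

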## 4.3 Analysis populations

The primary analysis will be performed according to the intention-to-treat (ITT) principle.

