#### **Modified intention to treat population (mITT)**

The mITT population will consist of all eligible randomized patients in the treatment group assigned by the randomization, irrespective of whether the patient underwent the procedure allocated by randomization or if crossovers occurred. Randomized patients who were later found to not meet inclusion criteria will not be included in the mITT population.

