## 5.2 Withdrawal/Follow-up

Criteria for stopping the study are:

- withdrawal of consent,
- liver transplantation,
- loss to follow up,
- enrollment of ineligible subjects.

Patients withdrawn from the study for withdrawal of consent, liver transplantation or loss to follow up will be censored at the date of withdrawal. Ineligible subjects will be excluded from the mITT analyses. Unless consent to analyze data is also withdrawn, all the data collected prior to withdrawal from the study will be considered for analysis.

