#### **Secondary endpoints**

Survival at Days 42, 90, 180 and 365

The survival rates will be compared with the same methods as described above for the analysis of composite event rate.

*Incidence of liver related death at Days* 42, 90, 180 and 365.

† ACLF: Acute on Chronic Liver Failure; **Grade 1:** a) Single kidney failure, b) Single liver, coagulation circulatory or respiratory failure + creatinine 1.5-1.9 mg/dL and/or HE I-II, c) Single cerebral failure (HE III-IV) + creatinine 1.5-1.9 mg/dL; **Grade 2:** 2 organ failures; **Grade 3:** 3 or more organ failure score.

The association of study arms with rebleeding hazard function will be tested using univariate and multivariate Cox models. The cumulative risk of rebleeding during follow-up in each arm will be estimated by calculating the cumulative incidence function (CIF) rebleeding at 12 months. In this approach, death for other causes during follow-up will be considered as a competing event.

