#### Survival analysis

All patients not reaching any event at the end of follow-up or before their last assessment (for patients lost to follow-up) will be censored at the date of their last assessment visit. Patients receiving a liver transplant will be censored at the time of liver transplantation.

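### Censoring control patients when they receive a TIPS for another indication departs from the intention-to-treat primary analysis and is missing from the survival censoring rules

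*SAP*

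**What the plan says.** The rule stands in SAP section 3.1, among the procedures for the control arm: when a TIPS is placed "for another indication during follow-up in the group B, the patient will be censured at the date of installation" of the device. No matching rule is given for group A. A salvage TIPS is treated separately, as a failure of the endoscopic procedure, with no censoring stated.

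The analysis sections read differently:

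- Section 4.3: "The primary analysis will be performed according to the intention-to-treat (ITT) principle". The mITT set keeps eligible patients in the assigned arm "irrespective of whether the patient underwent the procedure allocated by randomization or if crossovers occurred".
- Section 6.3, survival analysis, has two censoring rules. One begins "All patients not reaching any event at the end of follow-up or before their last assessment" and censors at the last assessment visit. The other is "Patients receiving a liver transplant will be censored at the time of liver transplantation".
- Section 5.2, under "Criteria for stopping the study are", lists withdrawal of consent, liver transplantation, loss to follow-up and enrolment of ineligible subjects. A later TIPS is not listed.
- Section 3.1 also says that "randomized patients are followed until the end of the 12-month study period".
- Section 6.2, on survival: "The survival rates will be compared with the same methods as described above for the analysis of composite event rate".

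**The concern.** Under intention to treat, a control patient who later receives a TIPS stays in the control arm and goes on contributing events. Under the section 3.1 rule the patient stays in the arm, but every death or rebleed after the device is dropped. These events are not missing: such a TIPS does not end study participation under section 5.2, and follow-up runs to 12 months.

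The trigger is a treatment decision made after randomization without blinding, and only control patients can meet it. Section 5.1 excludes patients who already have another indication for TIPS, so the indication arises or is recognized later, plausibly as the disease progresses. Kaplan-Meier, log-rank and Cox methods assume that censoring carries no information about prognosis, and here it may.

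The rule is not limited to the composite endpoint. With survival analysed by the same methods, it reaches all-cause death as written. An analyst who follows section 3.1 and one who follows sections 4.3 and 6.3 can report different control rates and hazard ratios.

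**Working it through.** **Text.** The rule is in section 3.1 and in neither list of censoring reasons (5.2, 6.3). Section 4.3 announces intention to treat. The crossover clause of the mITT definition mainly fixes who is in the set. It supports the point but is not itself a censoring rule.

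**Inputs from the SAP.** Section 3.3: 12-month event rates of 15% (TIPS) and 40% (glue), 52 patients per arm, 10% dropout. Section 4.1: two-sided tests at 0.05.

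- Hazard ratio: ln(0.85)/ln(0.60) = 0.318.
- Expected control events: 0.40 × 52 = 20.8.
- Standard error of a 40% rate in 52 patients: √(0.4 × 0.6/52) = 0.068, or 6.8 points.
- The planned size is not in dispute. Simulated with these inputs and no later TIPS, log-rank power is 88.8% one-sided and 81.4% two-sided, so the stated 80% one-sided is met.

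**Assumptions, because the SAP gives no frequency.** A fraction q of controls (2%, 5% or 10%) is due a TIPS at a uniform time in months 0–6 if still event-free. Their hazard is m times the usual one (m = 1 to 3), multiplied after TIPS by e. Here e = 1 means no effect and e = 0.318 is the SAP's own ratio. Hazards are calibrated so that the true control rate is 40% under intention to treat. Control rates come from Kaplan-Meier on 1,000,000 patients. Power comes from 40,000 simulated trials (simulation error about 0.2 points).

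| Scenario | q | Control rate under the rule | Power, ITT → rule | Significant under ITT only / rule only | Events dropped per 52 controls |
|---|---|---|---|---|---|
| Uninformative (m=1, e=1) | 2% | 39.9% | 81.6 → 81.3% | 0.95 / 0.65% | 0.30 |
| | 5% | 40.0% | 81.6 → 81.0% | 1.8 / 1.1% | 0.74 |
| | 10% | 40.0% | 81.2 → 79.9% | 2.9 / 1.7% | 1.47 |
| Higher risk, no TIPS effect (m=3, e=1) | 2% | 39.5% | 81.4 → 79.8% | 1.8 / 0.2% | 0.50 |
| | 5% | 38.7% | 82.1 → 77.9% | 4.5 / 0.3% | 1.24 |
| | 10% | 37.6% | 81.6 → 73.0% | 8.8 / 0.3% | 2.44 |
| Usual risk, effective TIPS (m=1, e=0.318) | 2% | 40.4% | 81.3 → 82.0% | 0.3 / 1.0% | 0.11 |
| | 5% | 40.9% | 81.5 → 83.4% | 0.4 / 2.3% | 0.27 |
| | 10% | 41.8% | 81.8 → 85.1% | 0.5 / 3.7% | 0.56 |
| Higher risk, effective TIPS (m=3, e=0.318) | 10% | 40.2% | 82.0 → 81.3% | 2.1 / 1.5% | 1.12 |

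**Discordant verdicts.** Losing follow-up changes some verdicts even when censoring is uninformative: 2.9 + 1.7 = 4.6% of trials at q = 10%. The worst case gives 8.8 + 0.3 = 9.1%, an excess of 9.1 − 4.6 = 4.5 points. What informative censoring mainly changes is which analysis wins.

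**Type I error** (both arms 40%, q of 5% and 10%, 60,000 trials): 4.9–5.2% under intention to treat and 5.0–5.5% under the rule.

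**Second check, other assumptions.** TIPS was uniform over the whole year in 5–15% of controls, with hazard ×1 or ×2 and post-TIPS hazard ×1 or ×0.4. There was no recalibration to 40%, and 5,000 trials were run per analysis. Control events lost ran from about 0.15 to 1.9 of about 20. The hazard ratio moved by −0.022 (0.354 to 0.332) to +0.007 (0.306 to 0.313). Two-sided power moved by +3.4 (77.0 to 80.4%) to −3.8 points (90.1 to 86.3%). The two analyses used separate samples, so these power differences carry an error of about √(2 × 0.8 × 0.2/5000) = 0.8 points.

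**The case against.** The rule is explicit, specific and prespecified, so it can be read as governing over a one-sentence principle. Section 6.3 does not claim to be exhaustive: withdrawal of consent is a censoring reason in 5.2 and is not named there. The one-arm form is largely structural, because group A receives its TIPS by design. Excluding patients with another indication at entry should make such TIPS rare. Censoring at the device could be a legitimate estimand, describing glue without later TIPS. The largest shifts need 10% crossover, triple hazard and a TIPS that does nothing, against the trial's own hypothesis. With an effective TIPS, total discordance is below the uninformative reference in all nine scenarios run, and power moves by only −0.7 to +3.3 points. The reference to the same methods for survival may mean only Kaplan-Meier, log-rank and Cox. The protocol, which is not shown, may not continue follow-up after such a TIPS.

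Much of this stands on size: the effect is modest and its direction unknown. The omission from 6.3, taken alone, would be a drafting matter. The rest does not remove the point. If the specific rule governs, the primary analysis is not the one section 4.3 announces. The SAP names no alternative estimand. Listing the rule in 6.3 would still leave a possibly informative, one-arm censoring rule in an analysis labelled intention to treat. Censoring at transplantation is a different case: it is a listed stopping criterion and applies to both arms.

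**Conclusion.** The concern holds. The conflict between the section 3.1 rule and the intention-to-treat principle is plain from the text and depends on no assumption.

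Its size does. For 2%, 5% and 10% of controls with such a TIPS, across all scenarios run:

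- the estimated control rate is 39.5–40.4%, 38.7–40.9% and 37.6–41.8%, so the largest shift (2.4 points) is well inside the 6.8-point sampling error;
- power is 80–82%, 78–83% and 73–85%, against about 82%;
- type I error is close to nominal.

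The rule hides control events if these patients are at higher risk and TIPS does not help them. It raises the control rate, in favour of early TIPS, if TIPS works as the SAP supposes. If such TIPS are rare, little changes. This should be corrected because the primary result ought not to depend on which section the analyst follows; it does not undermine the design.

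**What to change.** In the primary analysis, and in the survival analyses, count death and significant rebleeding to Day 365 in the assigned arm regardless of any later TIPS. Move censoring at a non-assigned TIPS to a labelled sensitivity analysis. Align sections 3.1 and 6.3 with section 4.3, so that 6.3 states how a later TIPS is handled.

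The cost is SAP wording and one sensitivity analysis, with no change to sample size. Section 3.2 describes randomization in the past tense, so recruitment may have begun. The change should therefore be dated and made before outcome data by arm are examined. If the protocol holds the same rule, it must be aligned. The fix needs events after TIPS to have been collected, as the 12-month follow-up statement provides. The small downside is that the primary contrast will include some control patients with a TIPS, as intention to treat implies.
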